### 1.3. Target Population – Asymptomatic Subjects at Risk for Alzheimer’s Dementia

In recent years the United States (US) National Institute for Aging and the International Working Group have proposed guidelines to better define the preclinical (asymptomatic) stages of AD. These working groups developed a hypothetical model for the pathophysiological process of AD that closely parallels the hypothetical biomarker model put forth by Jack et al. These models postulate that A $\beta$  accumulation begins many years before the onset of overt clinical impairment. The key risk factors for elevated amyloid accumulation and development of AD are age (ie, 65 years or older), apolipoprotein E (*APOE*) genotype, and family history. Approximately one third of clinically normal older individuals over 75 years of age demonstrate evidence of A $\beta$  accumulation on PET amyloid imaging studies or based upon CSF measurements. Similar findings are seen in large autopsy studies. These amyloid-positive (A $\beta$ +) clinically normal individuals consistently demonstrate evidence of an “AD-like endophenotype” on other biomarkers, including elevations in CSF tau and phosphorylated tau (p-tau), disrupted functional network activity in both functional magnetic resonance imaging (MRI) and resting state connectivity, fluorodeoxyglucose (F) (FDG) hypometabolism, cortical thinning, and accelerated rates of atrophy. Multiple studies have now reported that higher A $\beta$  burden in clinically normal individuals is associated with evidence of subtle decreases in cognitive performance over time with changes that can be detected even within the range of “normal” values. The accumulating longitudinal data also strongly suggests that A $\beta$  clinically normal individuals are at increased risk for cognitive decline and progression to mild cognitive impairment (MCI) and AD dementia. Several published studies from the Alzheimer’s Disease Neuroimaging Initiative (ADNI), Australian Imaging Biomarker and Lifestyle (AIBL), and Mayo Clinic have confirmed a faster rate of cognitive decline in A $\beta$  clinically normal individuals. The Alzheimer’s scientific community is of the consensus that these A $\beta$  clinically normal individuals represent an early stage in the continuum of AD pathology.

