### Exploratory Objectives

The exploratory objectives of this study are the following:

- To investigate the effect of atabecestat compared with placebo on brain volume as measured by volumetric MRI.
- To investigate the impact of atabecestat compared with placebo on markers of synaptic dysfunction on task-free functional MRI.
- To assess the effects of atabecestat on additional downstream markers of neuronal injury, neurodegeneration, or inflammation in CSF compared with placebo.
- To assess the effects of atabecestat on progression of tau spreading pathology in the brain as measured by tau PET imaging.
- To explore if baseline markers of neurodegeneration (eg, volumetric MRI, CSF t-tau or p-tau, or tau PET) are related to cognitive decline and response to treatment with atabecestat.
- To explore the correlation between the effect of atabecestat on biomarkers (eg, amyloid PET, plasma A $\beta$ , CSF A $\beta$  and t-tau or p-tau, tau PET) and clinical outcomes.
- To explore the impact of disclosure of amyloid status on questionnaires probing subject perception of amyloid imaging and concern about developing AD dementia.
- To investigate the effect of atabecestat compared with placebo on cognition as measured by a computerized cognitive battery.
- To investigate the effect of atabecestat compared with placebo on function as measured by the Financial Capacity Instrument (FCI).
- To investigate the effect of atabecestat compared with placebo on medical resource utilization as measured by the Healthcare Resource Utilization Questionnaire (HRUQ) scale.

- To investigate the effect of atabecestat compared with placebo on health outcomes as measured by the Short Form-36 (SF-36) and European Quality of Life-5 Dimensions 5-level (EQ-5D-5L) scales.
- To explore the ability of the Cognitive Function Index-acute (CFI-a) to measure decline of cognitive function and performance of everyday activities.
- To explore the effect of atabecestat compared with placebo on instrumental activities of daily life (IADL) as measured by the Amsterdam IADL questionnaire (A-IADL-Q).

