### 4.1. Inclusion Criteria

Each potential subject must satisfy all of the following criteria to be enrolled in the study.

1. Subject must be a man or woman 60 to 85 years of age, inclusive, at time of informed consent. Subjects 60 to 64 years of age must also have 1 of the following 3 conditions:
  - a. A positive family history for dementia (minimum of 1 first degree relative)
  - b. A previously known *APOE*  $\epsilon$ 4 genotype
  - c. A previously known biomarker status demonstrating elevated amyloid accumulation in CSF or PET
2. Subjects must have a global CDR score of 0 at screening.
3. Subjects must be able to read and write and must have adequate hearing and visual acuity to complete the psychometric tests. The legally acceptable representative must also be able to read and write.
4. Subjects must have evidence of elevated amyloid accumulation by means of either:
  - a. Low CSF  $A\beta_{1-42}$  levels at screening
  - b. A positive amyloid PET scan at screening (depending on the site's PET capability)

*Note: The cut-off value for CSF  $A\beta_{1-42}$  will be based on the value established by the central CSF screening laboratory and specified in a separate laboratory manual. Screening amyloid PET scans will be assessed centrally by a qualified reader for inclusion based on predefined criteria as documented in the imaging manual.*
5. Subjects must be otherwise healthy for their age group or medically stable with or without medication on the basis of physical examination, medical history, vital signs, and 12-lead ECG performed at screening or at baseline.
6. Subjects must be otherwise healthy or medically stable on the basis of clinical laboratory tests performed at screening. If the results of the serum chemistry panel, hormones (thyroid tests), hematology, or urinalysis are outside the normal reference ranges, the subject may be included only if the investigator judges the abnormalities or deviations from normal to be not clinically significant, to be appropriate and reasonable for the population under study, and not to be a potential cause of cognitive impairment. For low vitamin B12 and abnormal thyroid hormone tests, enrollment requires written approval from the sponsor's medical monitor.

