**Evidence of elevated amyloid accumulation (Step IV)** will be assessed by either (1) a CSF sample for determination of A $\beta$ 1-42 concentration or (2) an amyloid PET scan for determination of cerebral fibrillar amyloid. Subjects can have both CSF collection and amyloid imaging performed (the aim is that approximately 20% of subjects will have both screening biomarker evaluations to better understand concordance of the biomarkers in screening and treatment). Amyloid status for study entry will be based on at least 1 of these biomarkers confirming elevated amyloid accumulation. It is sufficient to demonstrate elevated amyloid accumulation by 1 of the 2 markers, but the decision to perform 1 or both needs to be made before either result is available. The amyloid disclosure visit will be performed when both results, if applicable, are available. Subjects with negative results for both biomarker tests of elevated amyloid accumulation cannot be rescreened. Subjects who elect up front to be tested on only 1 of the biomarkers cannot be screened for the other if their results are negative, unless the decision is made before either result is available.

All subjects who undergo the **Step IV** amyloid burden assessment will have their results disclosed during a separate in-clinic **amyloid status disclosure visit** conducted during the screening period by a clinical investigator approved for this role. This visit must take place at least 2 days prior to the baseline cognitive assessments. Disclosure of the amyloid accumulation results will be per local laws and regulations. Informant attendance is not required at this visit, but may be permitted if the subject agrees. Subject concern about developing AD and his/her views and perceptions of amyloid imaging, as well as perception of future time, will be repeated following disclosure of amyloid status using the questionnaires specified above for Step I. The Impact of Events Scale (IES) will be administered over the phone (or at a visit) within 3 days following the amyloid status disclosure visit.

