**9.5.5. Impact of Events Scale**

The IES is a 15-item self-report measure that assesses 2 common responses related to a specific stressful life event: intrusion and avoidance. It is a reliable scale that can be anchored to any specific life event and permits assessment of individuals over time, comparison of the degree of distress among subgroups, and comparison of the impact of various events. The IES has been anchored to test-related distress in previous genetic testing studies and has been adapted for amyloid disclosure-related distress. The instrument asks subjects to respond to statements related to the stressful event (ie, disclosure of amyloid results) with ratings of 0 (not at all) to 5 (often). The IES will be administered by study staff to all subjects by telephone within 3 days after disclosure of amyloid status during the screening phase.

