2.6. Analysis Sets

2.6.1. Efficacy Analysis Sets

2.6.1.1. Primary Efficacy Analysis Set

The primary efficacy analysis set includes all randomized subjects (intent-to-treat [ITT] analysis set).

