4. SUBJECT INFORMATION

The ITT analysis set and the safety analysis set will be used throughout this document. The number of subjects screened and the number of subjects in each analysis set will be summarized by treatment group and overall. In addition, the distribution of subjects by region, country, and site will be presented. Region is defined as found at <http://unstats.un.org/unsd/methods/m49/m49regin.htm>.

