4.1.9. Amyloid Disclosure Assessments

The Concerns about Alzheimer’s Disease Dementia Scale and the Future Time Perspective Scale are conducted for all subjects during the screening phase prior to and after the amyloid status disclosure visit and at regularly scheduled visits during the double-blind phase. For subjects with a PET scan performed to assess eligibility, the Views and Perceptions of Amyloid Imaging Scale will be assessed during the screening phase prior to and after the amyloid status disclosure visit. The Impact of Events Scale will be assessed for all subjects during screening after the amyloid status disclosure visit.

Concerns about Alzheimer’s Disease Dementia Scale

See Section 5.5.1.1 for details about the Concerns about Alzheimer’s Disease Dementia Scale. The distribution of item scores, which range from 1 (strongly agree) to 5 (strongly disagree), for each of the 6 questions will be summarized by treatment group and overall for the pre- and post-amyloid status disclosure visits.

Future Time Perspective Scale

See Section 5.5.1.1 for details about the Future Time Perspective (FTP) Scale and calculation of the overall FTP score. Overall FTP score will be summarized with descriptive statistics by treatment group and overall for the pre- and post-amyloid status disclosure visits.

Impact of Events Scale

The Impact of Events (IES) scale is a 15-item self-report measure that assesses 2 common responses related to a specific stressful life event: intrusion and avoidance³. The IES has been adapted for amyloid disclosure-related distress. The scale will be administered during the screening phase within 3 days after disclosure of amyloid status.

Subjects will rate how frequently each item was true for them since disclosure of amyloid results as “not at all” (0), “rarely” (1), “sometimes” (3), or “often” (5). The Intrusion sub-scale is the sum of the scores of the 7 intrusion-related items and the Avoidance sub-scale is the sum of the scores of the 8 avoidance-related items (see [Attachment 4](#) for a list of which items belong to which sub-scale). The total score is the sum of all 15 items. If any item is missing, the relevant sub-scale and the total score will be missing.

The total IES score and the Intrusion and Avoidance subscales will be summarized with descriptive statistics by treatment group and overall.

Views and Perceptions of Amyloid Imaging Scale

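### The amyloid-disclosure objective has no planned paired pre-to-post change, and amyloid-negative subjects who were also told their result appear in no questionnaire table

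*Protocol*

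**What the plan says.** The objective, in Protocol 2.1 and again in SAP 1.1.3, is "To explore the impact of disclosure of amyloid status on questionnaires probing subject perception of amyloid imaging and concern about developing AD dementia". Protocol 9.5.6 adds that the Future Time Perspective scale is repeated to see whether disclosure altered the subject's outlook.

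**Who is told, and who is asked.** Under Protocol 9.1.2, all subjects who have the Step IV "amyloid burden assessment will have their results disclosed during a separate in-clinic" visit. Protocol 9.5.4 and 9.5.6 schedule the Concerns and Future Time Perspective scales for all subjects before and after disclosure. Protocol 9.5.3 does the same for the Views scale in those screened by PET. For the IES, Protocol 9.5.5 states: "The IES will be administered by study staff to all subjects by telephone within 3 days after disclosure of amyloid status".

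**Who is analysed.** SAP 4 states: "The ITT analysis set and the safety analysis set will be used throughout this document". Both sets contain only randomised subjects (SAP 2.6.1.1 and 2.6.2), and under Protocol 4.1 "Subjects must have evidence of elevated amyloid accumulation by means of either" CSF or PET. For screen failures, SAP 4.2 plans only counts and reasons.

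**What is tabulated.** SAP 4.1.9 summarises the Concerns, Future Time Perspective and Views scales at the pre- and post-disclosure visits, by treatment group and overall. For the IES: "The total IES score and the Intrusion and Avoidance subscales will be summarized with descriptive statistics by treatment group and overall".

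**The concern.** The objective asks what disclosure does to the subject's perceptions and concerns. Answering it takes at least a within-subject change across the disclosure visit. Preferably it also takes some reference for how much these scores move when a subject is simply re-tested some weeks later, having been through testing and a results visit.

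The SAP specifies neither. The reader gets two marginal distributions per scale in amyloid-positive subjects, plus one post-disclosure distress score. Subjects who went through the same testing and disclosure but received the other result are a natural reference group. The protocol schedules them for the same questionnaires, yet no table reports them. At stake is whether the trial uses these screening data to address its own exploratory question.

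**Working it through.** Neither document gives a sample size, power or error rate for this objective, so there is no planned figure to reproduce. The check is mainly one of tracing the rules.

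**1. Order of events.** The disclosure visit is at least 2 days before the baseline cognitive visit, which falls between Day -10 and Day -5 (Time and Events Schedule, Screening Phase). The latest disclosure day is therefore -5 - 2 = Day -7. Randomisation is on Day 1 (Protocol 9.1.3). Arm cannot influence any screening-phase questionnaire, so differences between arm columns there are chance.

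**2. Population.** SAP 4 uses the ITT and safety sets, both sets are randomised subjects only, and randomised subjects are amyloid-positive by inclusion criterion 4. SAP 4.1.9 names no analysis set of its own. The restriction is read from SAP 4 and from the by-treatment-group layout, which an unrandomised subject cannot enter.

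**3. Does a later change score fill the gap?** SAP 5.5.1.1 calculates change from baseline for the Concerns items and the Future Time Perspective scores. SAP 2.4 (Table 1) defines baseline as the visit closest to Day 1 within Days -120 to 1. Both scales are given in screening Step II, then after disclosure, and next at Month 1. The assessment closest to Day 1 is the post-disclosure one, so the change score begins after the disclosure step. SAP 5.5.2 directs any inference on exploratory endpoints at the treatment effect.

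**4. The IES.** It is given once, within 3 days after disclosure, with items anchored to the disclosure. Protocol 9.5.5 supports the scale partly because it allows distress to be compared between subgroups. The subgroup split by amyloid result is not planned.

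**5. Illustrative precision.** This is in units of the SD of the pre-to-post change and assumes complete questionnaires.

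- Paired change, all 557 randomised (SAP 1): 1.96/√557 = 0.083.
- Paired change, one arm (557/3 ≈ 186): 1.96/√186 = 0.144.
- Elevated minus not elevated: 1.96 × √(1/557 + 1/n), with n = 557 × (1 - p)/p and p the share of tested subjects who are positive.

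| Assumed p | n not elevated | 95% half-width |
|---|---|---|
| 20% | 2,228 | 0.093 |
| one third | 1,114 | 0.102 |
| 45% | 681 | 0.112 |

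The only prevalence figure used here is in Protocol 1.3: "Approximately one third of clinically normal older individuals over 75 years of age demonstrate evidence of" amyloid accumulation. It applies to an older group than the 60 to 85 years enrolled, so p is an assumption and a range is shown.

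**The case against.** The best reply is that the SAP already does something reasonable. The Views and Concerns scales, which the objective names, are shown before and after disclosure, and so is Future Time Perspective. Every scale has an overall column as well as arm columns. Describing how the trial population reacted is a fair reading of an exploratory objective. All of this stands, and it rules out the reading that there is no comparator at all or that the data are shown only by arm.

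A reader might also infer that the IES can show no impact because it has no pre-disclosure value. The documents do not support that. Its items ask about the period since disclosure, so a pre-disclosure score would mean little, and the scale does describe distress tied to the event. What it cannot do here is distinguish an elevated result from testing and disclosure in general. It measures distress, so it is only loosely within an objective about perception and concern.

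Nor do the arm columns need to go. They sit among the baseline characteristics in SAP 4.1, no by-arm contrast is planned for these screening data, and two of the scales continue as exploratory endpoints.

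An elevated versus not-elevated contrast is unrandomised, and it estimates the effect of the result, not of disclosure. That stands, and the table should say so.

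Finally, SAP 1 says that the study objectives cannot be evaluated after the early stop. The reason it gives is the reduced sample size. These data are collected before dosing, and the SAP still lists the objective and tabulates the scales. The stop lowers the priority of the point but does not remove it.

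**Conclusion.** The point holds in a limited form. For an objective about disclosure, the plan estimates no pre-to-post change. It also omits the amyloid-negative subjects who were told their result and are scheduled for the same questionnaires. Pre/post shifts in the planned tables are therefore confounded with re-test and time effects, and the IES score has no reference group.

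This is an inexpensive improvement to an exploratory, descriptive analysis. It changes no primary, secondary or safety conclusion.

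The conclusion rests on reading SAP 4 as governing SAP 4.1.9. The precision figures are illustrative only, for three reasons:

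- The positivity rate is assumed.
- Questionnaire completion among screen failures is not given.
- The 557 randomised are not all the disclosed positives. The Amendment 5 rationale describes subjects who failed screening after learning their amyloid status.

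**What to change.** In SAP 4.1.9:

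1. Add the overall paired change from the pre- to the post-disclosure visit, with 95% CI, for the Concerns items, the Future Time Perspective score and, in PET-tested subjects only, the Views items.
2. Add a descriptive summary in all screened subjects with a disclosure visit and questionnaire data, by amyloid result (elevated or not elevated). Give the IES total and subscales and the pre/post changes, each with the between-group difference and 95% CI. Report questionnaire completion in each group. Label the contrast observational, and state that it concerns the result disclosed, not disclosure itself.

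The existing by-arm and overall columns can stay as a baseline display.

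Before any change is computed, settle the item coding. The Concerns anchors run in opposite directions in SAP 4.1.9 and SAP 5.5.1.1. The Views scale starts at 0 in SAP 4.1.9 but at 1 in Protocol 9.5.3.

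The cost is SAP wording and a few tables that include screen failures. The protocol already schedules the questionnaires, but the sponsor should confirm that the screen failures' responses are in the database. The downside is an unrandomised contrast that must be read with care.

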## **2.2. Hypotheses**

[figure not shown]
The primary hypothesis is that cognitive decline, as measured by the PACC change from baseline at Month 54 (Year 4.5), will be significantly less for subjects treated with either atabecestat dose in comparison to subjects treated with placebo. The key secondary hypothesis is that functional decline, as measured by the CFI change from baseline at Month 54 (Year 4.5), will be significantly less for subjects treated with either atabecestat dose in comparison to subjects treated with placebo.

## **3. STUDY DESIGN AND RATIONALE**

### **3.1. Overview of Study Design**

This is a multi-center, double-blind, placebo-controlled, randomized, parallel-group study assessing the efficacy and safety of atabecestat over approximately 4.5 years of treatment in subjects (60 to 85 years of age) who are asymptomatic and at risk for developing Alzheimer's dementia due to evidence of elevated amyloid accumulation based on CSF or amyloid PET imaging (see Section 3.2.2 and complete definition of study population in Section 4).

The study will consist of 3 phases: a screening phase of approximately 90 days during which subject eligibility will be assessed; a fixed dose, double-blind treatment phase during which eligible subjects will receive randomly assigned study drug once daily for up to 4.5 years; and a follow-up phase to be conducted 7 to 28 days after the last dose of study drug. This study will be conducted in an outpatient setting. The maximum study duration for a subject will be 58 months (3-month screening phase + 54-month double-blind treatment phase +1-month follow-up phase). A diagram of the study design is provided in [Figure 2](#).

**Figure 2: Schematic Overview of Design for Study 54861911ALZ2003**

### Continuous safety monitoring by DMC + Interim biomarker analyses

DMC=Data Monitoring Committee; FPD=first patient date; IA=interim analysis; SSR=sample size re-estimation.

Subjects who meet all of the study inclusion criteria (Section 4.1) and none of the study exclusion criteria (Section 4.2) will be assigned randomly to 1 of 3 treatment groups in a 1:1:1 ratio at the start of the double-blind treatment phase: atabecestat 5 mg, atabecestat 25 mg, or placebo (see Section 3.2.3 for dose selection rationale). Approximately 1,650 subjects (550 per treatment group) will be randomized in order to achieve a total of 1,155 subjects (385 per treatment group) who complete the Month 54 (Year 4.5) assessments (assumed 30% attrition rate per treatment group), as outlined in Section 11.2. The number of subjects randomized can be increased based on blinded sample size re-estimation, but the study enrollment will be capped at 2,400 subjects. At randomization, subjects will be stratified by country, and by apolipoprotein E (*APOE*)  $\epsilon 4$  carrier status (carrier vs noncarrier) (see Section 5).

In addition to longitudinal follow-up of subjects' screening biomarker(s) (ie, amyloid PET and/or CSF), subjects will have the opportunity to participate in 1 or more longitudinal PD substudies: CSF for biomarkers and drug exposure, amyloid PET imaging, and tau PET imaging (see Section 3.2.6). Longitudinal tau PET imaging will be open to all subjects enrolled at sites having access to this technology, and subjects who elect to undergo these assessments will provide separate informed consent for this procedure. When sufficient longitudinal biomarker data has been collected, further collection of biomarker data can be terminated to reduce patient and site burden.

An informant (eg, relative, partner, or friend) will be used in this study (see Section 4.1, Inclusion Criterion 7). The informant will provide subject information on clinical scales, and may help with handling and dispensing of study drug, or reporting of AEs. Because of the informant's critical role for several endpoints, a second, replacement informant should be identified, preferably prior to Day 1.

Some design elements of this Phase 2b/3 study can be modified during the trial based on emerging external data. The potential changes include optimization of the primary endpoint and

the timing of the primary analysis. Sample size may be adjusted based on review of blinded aggregated study data. Unblinded interim analyses (IAs) may be performed to assess futility.

An independent DMC will be commissioned for this study to review safety and other relevant data on an ongoing basis, and to review findings from the potential IAs and make recommendations based on prespecified decision rules. (see Section 11.11).

